Turner's syndrome (TS), 45 X, and primary ovarian insufficiency (POI), 46,XX are both conditions that result in severe estrogen deficiency in young women. TS is an X-chromosomal defect that results in ovarian dysgenesis and lifelong estrogen deficiency. These women have a reduced life expectancy with the main cause of death being cardiovascular complications including a seven-fold higher rate of CVD. Additionally, women with TS have higher rates of CVD risk factors including hypertension, hyperlipidemia, diabetes, and obesity. Another model of severe estrogen deficiency in young women is 46, XX primary ovarian insufficiency (POI) resulting in primary amenorrhea. In a cross-sectional study of women in their early 30's with estrogen deficiency, either TS or POI, a statistically significantly thicker cIMT (mm) was found in TS and POI women compared to normal controls of similar ages. $(0.61 \pm 0.07 \text{ mm}; 0.60 \pm 0.05, \text{ and } 0.55 \pm 0.06, \text{ p<}0.001, \text{ respectively}).^{22}$

- **B.5.** CVD risk in women with premature estrogen loss is attenuated by estrogen therapy. Estrogen therapy reduces oophorectomy-related and POI CVD risk, ^{23-28,29} Estrogen therapy in young TS and POI results in improved high density lipoprotein cholesterol (HDL-C), serum glucose and cIMT. These important observational findings suggest that estrogen modulates CVD in young women with HypoE.
- **B.6.** Premenopausal HypoE due to Functional Hypothalamic Amenorrhea (FHA) may contribute to CVD risk. HypoE in premenopausal women is most often due to FHA; up to one third of adult-onset amenorrhea is due to estrogen disruptions.³⁰ FHA is defined as no menses

due to low estrogen due to suppression of the hypothalamic-pituitary-ovarian axis and excludes pathologic diseases such as those related to a systemic disease or associated with a disorder of the reproductive tract. FHA is due to suppression of the hypothalamic gonadotropin-releasing hormone (GnRH) pulsatility resulting in lower levels of follicle stimulating hormone, luteinizing hormone, and a state of estrogen deficiency. There are 3 types of FHA associated with stress, weight loss, or excessive exercise.

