- C.1.1. Recruitment: Women with HypoE, normal controls and recently postmenopausal woman will be recruited from several different locations including the Women's Hormone and Menopause Program at the Barbra Streisand Women's Heart Center, Center for Fertility and Reproductive Medicine in the Department of Obstetrics and Gynecology at Cedars-Sinai Medical Center (CSMC) and CSMC OB/GYN staff physician's offices by posting the study flyer in waiting rooms. We also plan to recruit women from the community by posting our study flyer on community bulletin boards at local college campuses, gyms and yoga studios as well as expand the social media posting to social media. I will also contact student health centers and obtain permission to post the study flyer at these locations. (see study flyers) To determine if a self-identified woman has HypoE, we will provide screening laboratories: FSH, LH, estradiol, progesterone, TSH, Free T4, prolactin, testosterone, free testosterone and androstenedione. Beta-HCG by urine or serum to ensure negative pregnancy prior to enrollment. These screening labs will be performed after a woman has signed the consent form. If a woman has already seen a physician and has had these laboratory results performed, we plan to use that report and not perform additional labs. For women who qualify as HypoE, they will return within 7 days for a repeat estradiol blood draw to confirm HypoE. Regularly cycling women will be (age- and BMImatch) defined as having self-reported menstrual cycle lengths of 24 to 38 days not on hormone therapy, and confirmation of one ovulation by either urinary LH surge or day 22-26 progesterone > 3 ng/ml. If ovulation is not confirmed that month, i.e. progesterone < 3 ng/ml then we would rescreen the subsequent month. Beta-HCG by urine or serum to ensure negative pregnancy prior to enrollment. For recently postmenopausal women will be determined by FSH>30 and 12 months of amenorrhea, 40 within 3 years of final menstrual period with natural menopausal not on hormone therapyFinally, we will offer a one-time \$50 stipend to normal control and menopausal women, for the HypoE women up to \$300 stipend will be offered for their research visit and time commitment. I have developed a pre-screening questionnaire which includes questions regarding the inclusion and exclusion criteria (see below). For this project, I will recruit 30 women with premenopausal HypoE. 30 regularly cycling women and 30 postmenopausal women.

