- **C.1.2.** Eligibility/Inclusion Criterion: *Entry criteria* for HypoE and normal controls will include premenopausal by WISE criteria currently not on hormone therapy, English speaking (for the purposes of complete psychosocial assessment), able to give informed consent, a gynecological age (age since menarche) > 10 and < 25 years, and chronological age > 18 years. Within 90-110% of ideal body weight as determined by the 1983 Metropolitan height and weight table for women. All patients with hypothalamic amenorrhea will be diagnosed based on exclusion of other etiologies for their amenorrhea, including pregnancy, thyroid dysfunction, hyperprolactinemia, POI, and polycystic ovary disease. For recently postmenopausal women will be determined by FSH>30 and 12 months of amenorrhea, and within 3 years of final menstrual period with natural menopausal not on hormone therapy, English speaking, able to give informed consent.

Exclusion criteria for normal control and postmenopausal groups are current use of hormone contraceptive or any estrogen or progestin therapy, smoking, hypertension, hyperlipidemia, diabetes, medical, neurological, or ophthalmologic disease except acuity problems, a major Axis I disorder other than depression, parturition in the last 12 months and/or lactating in the last 6

months or the patient has any concurrent disease or condition that in the opinion of the investigator would make the patient unsuitable for participation in the study.

[figure not shown]
For HypoE women, exclusion criteria includes current use of hormone contraceptive or any estrogen or progestin therapy, allergy to adhesive or tape allergy, or the patient has any concurrent disease or condition that in the opinion of the investigator would make the patient unsuitable for participation in the study.

For postmenopausal women exclusions also include surgical or chemotherapy induced menopause or premature ovarian failure.

- **C.1.3. Data Collection:** All laboratory data will be collected and analyzed according to our published WISE Core Lab methods.⁴¹ Data collection will occur at the Cedars-Sinai Women's Heart Center. Collection will include: reproductive hormone assays (estradiol, progesterone, FSH, LH, bioavailable testosterone, fasting lipid panel (LDL, HDL, Trigylcerides) and metabolic and inflammatory markers (glucose, cortisol, hsCRP). Blood pressure, pulse and body mass index computed as weight in kg/height in m² will be collected.

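### Hypertension and hyperlipidemia exclude women from the comparison groups but not from the HypoE group, which can bias the Aim 1 blood pressure and LDL comparison with cycling controls toward HypoE looking worse, probably by a small amount

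*Combined protocol and SAP*

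**What the plan says.** Section C.1.2 of the combined protocol and SAP has one exclusion list for the two comparison groups and another for HypoE women.

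- Regularly cycling and postmenopausal women: "Exclusion criteria for normal control and postmenopausal groups are current use of hormone contraceptive or any estrogen or progestin therapy, smoking, hypertension, hyperlipidemia, diabetes". The list continues with "medical, neurological, or ophthalmologic disease except acuity problems, a major Axis I disorder other than depression, parturition in the last 12 months", lactation, and an investigator-opinion clause.
- HypoE women: "For HypoE women, exclusion criteria includes current use of hormone contraceptive or any estrogen or progestin therapy, allergy to adhesive or tape allergy", followed by the same investigator-opinion clause. Smoking, hypertension, hyperlipidemia and diabetes are not named. The entry criteria shared with cycling women do not name them either.

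Two other passages restrict disease in HypoE women. Section B.6 defines FHA as a condition that "excludes pathologic diseases such as those related to a systemic disease or associated with a disorder of the reproductive tract". Section C.1.2 requires amenorrhea to be "diagnosed based on exclusion of other etiologies for their amenorrhea, including pregnancy, thyroid dysfunction, hyperprolactinemia, POI, and polycystic ovary disease". Neither mentions the four conditions.

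Aim 1 compares systolic and diastolic pressure, LDL and other markers, with the hypothesis that HypoE women are worse. Cycling controls are matched on age and BMI (C.1.1), and they share a weight criterion of 90-110% of ideal with HypoE women (C.1.2). There are to be 30 women per group. The document has no Aim 1 analysis section: C.3.5 refers to a description under Aim1A that is not there.

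**The concern.** Hypertension and hyperlipidemia are the adverse ends of blood pressure and blood lipids. A rule that removes those ends from the cycling controls and leaves them in the HypoE group selects on the outcome, in the direction of the hypothesis. Matching on age and BMI cannot undo that, because women of the same age and BMI are still kept or dropped according to the outcome. The investigator-opinion clause stands in both lists, so it does not even them out.

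What is at stake is attribution. Part of any blood pressure or LDL difference from cycling women could come from the eligibility rule and not from low estrogen. Triglycerides are affected in the same way only if hyperlipidemia, which is not defined, covers them. HDL, hsCRP and PAT could be affected only indirectly, through conditions that remain in the HypoE group.

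**Working it through.** **The plan's own figure.** The plan gives no power or error figure for Aim 1. Its one power statement, for Aim 3 (C.3.5), reproduces: SD of change = √(0.44² + 0.44²) = 0.622, and a two-sided t test with 15 + 15 women, alpha 0.0167 and 80% power detects 0.775, stated as 0.78. The present point does not depend on it.

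**Inputs.** From the documents: 30 against 30, the two exclusion lists and the Aim 1 outcomes. Assumed: a normally distributed marker, no true difference, Welch t test at two-sided 0.05 (no Aim 1 level is stated), a share p of women above the cut, and a fraction f of those actually excluded from the controls. f = 1 is a sharp cut on the measured value. f = 0.5 means that half are missed. The second case matters because the screening tests in C.1.1 are hormonal ("we will provide screening laboratories: FSH, LH, estradiol, progesterone, TSH, Free T4, prolactin, testosterone, free testosterone and androstenedione"), with no lipids or blood pressure, so exclusion may rest on known diagnoses.

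**Gap.** With z the cut and φ the normal density, the control mean falls by f·φ(z)/(1 − f·p) SD. For p = 0.05, z = 1.645 and φ(z) = 0.1031. Then f = 1 gives 0.1031/0.95 = 0.109, and f = 0.5 gives 0.0516/0.975 = 0.053. Error rates are simulated, with a nominal 2.5% in this direction.

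| p | gap, f = 1 | false HypoE worse | gap, f = 0.5 | false HypoE worse |
|---|---|---|---|---|
| 1% | 0.027 | 3.1% | 0.013 | 2.8% |
| 2% | 0.049 | 3.8% | 0.024 | 3.0% |
| 5% | 0.109 | 6.1% | 0.053 | 3.9% |
| 10% | 0.195 | 12% | 0.092 | 5.4% |

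At 0.0167 (the Aim 3 level; nominal 0.83%), p = 2%, 5% and 10% give about 1.3%, 2.3% and 5% with f = 1, and 1.0%, 1.4% and 2.0% with f = 0.5. For scale, 30 against 30 has 80% power for about (1.960 + 0.842)·√(2/30) = 0.72 SD.

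**Treatment.** The table leaves HypoE women at untreated values. C.1.2 does not exclude HypoE women on blood pressure or lipid treatment. Take f = 0.5 and suppose that the diagnosed HypoE women are treated.

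- Treated down to the cut, the gap falls by f·[φ(z) − p·z], to 0.021, 0.042 and 0.069 SD at p = 2%, 5% and 10%.
- Treated to the population mean, it falls by f·φ(z), to about 0.000, 0.001 and 0.005 SD.

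**Postmenopausal comparison.** These women are older and not matched, and B.3 says that risk factors worsen after 50. A disadvantage of about 0.06, 0.14 or 0.29 SD in that group would cancel the sharp-cut gap at p = 2%, 5% or 10%. The net direction cannot be settled from the documents.

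**Effect of restricting the HypoE group.** With the same rule in both groups and no true difference, the gap is zero. With a true shift of 0.5 SD, let q be the share of HypoE women above the cut. Their restricted mean is (0.5 − f·[0.5q + φ(z − 0.5)])/(1 − f·q), and the control gap is added. For p = 10% and f = 1, q = 0.217, so (0.5 − 0.109 − 0.294)/0.783 ≈ 0.12, and 0.12 + 0.195 ≈ 0.32. Over p = 2%, 5% and 10% the result is 0.42, 0.37 and 0.32 SD (f = 1) or 0.46, 0.44 and 0.43 SD (f = 0.5).

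**Mismatched rules.** If controls are excluded on diagnosis (f = 0.5) but HypoE women are restricted on measured values (f = 1), the gap reverses to −0.025, −0.056 and −0.103 SD at the same p.

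**The case against.** The strongest reply is that leaving HypoE women unrestricted is defensible. Section B.4 treats dyslipidemia and hypertension as consequences of low estrogen, so excluding them would remove part of the effect under study. That stands. It is why the restricted comparison should be a sensitivity analysis and not a replacement.

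The size is also likely to be slight. The women are young and near ideal weight, and treated HypoE women may contribute almost no gap. That stands too, and it decides the severity.

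A reader might infer that the asymmetry could never be examined afterwards. The documents do not support this. Section C.1.3 collects blood pressure, "fasting lipid panel (LDL, HDL, Trigylcerides) and metabolic and inflammatory markers (glucose, cortisol, hsCRP" and does not limit this to any group, so a restriction on measured values would be possible for three of the four conditions, though imperfect for treated women. Smoking, diagnoses and treatment are not listed there. Two cautions apply: C.1.3 may not be a complete list, since C.1.2 mentions a psychosocial assessment that C.1.3 omits; and C.1.1 says "I have developed a pre-screening questionnaire which includes questions regarding the inclusion and exclusion criteria", which may put these questions to everyone, but its content is not shown.

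A reader might also infer that all four conditions have been shown to shift blood pressure and LDL. The calculation models one cut on one marker. The effects of smoking and diabetes are not quantified, so the sharp-cut figures do not bound the whole rule.

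Dropping the blood pressure and lipid exclusions from the comparators would be symmetric as well and would truncate neither group. It would change who is recruited, which the sensitivity analysis does not.

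**Conclusion.** The point holds as a minor one. The two lists differ on the page, two of the conditions overlap with Aim 1 outcomes, and nothing in the plan corrects for it. The rule can therefore bias the blood pressure and LDL comparison with cycling controls toward HypoE looking worse. The likely size is at the low end: about 0.01-0.05 SD, with a one-directional error of about 3-4% against 2.5%, if 1-2% of women are above the cut. It reaches about 0.2 SD and 12% only at 10% with a sharp cut. All of this rests on assumed prevalences, one normally distributed marker, no true difference and untreated values. With treatment the gap shrinks and may be close to nil.

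It would go too far to conclude that a HypoE disadvantage in Aim 1 would be an artefact, that the comparison with postmenopausal women is biased in a known direction, or that the trial's treatment effect is compromised. Aim 3 randomises within the HypoE group, so this asymmetry does not bias it.

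**What to change.** 1. In all three groups and from the same source, record smoking, known hypertension, hyperlipidemia and diabetes, and any blood pressure or lipid treatment. Report the counts by group. Define hyperlipidemia.
2. Add the missing analysis text for Aims 1 and 2. In it, prespecify a sensitivity comparison restricted to HypoE women who meet the comparators' exclusions for these four conditions. Apply one rule in every group, diagnosis against diagnosis or measured value against measured value, because mixing them reverses the bias.
3. Show the restricted comparison beside the unrestricted one, label the latter as asymmetric, and do not attribute a blood pressure or LDL difference to HypoE without showing both.
4. State that the restricted comparison understates a true effect on blood pressure or lipids, given B.4.
5. Keep all 30 HypoE women in Aim 3.

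The cost is a few data fields and a paragraph, but the paragraph needs an Aim 1 analysis section to sit in, and that has to be written first. The restricted comparison also loses women and power. If each condition is present in 2%, 5% or 10% (assumed) and there is no true difference, between p (complete overlap) and 1 − (1 − p)⁴ (independence) leave: 2-8%, 5-19% or 10-34%. A true 0.5 SD falls to about 0.32-0.46 SD. In the worst case (sharp cut, independent conditions, a true 0.5 SD shift in both blood pressure and LDL), 1 − (1 − q)²(1 − p)² = 15%, 31% or 50% leave, with q = 6.0%, 12.6% or 21.7%. That leaves 25, 21 or 15 HypoE women and power of about 39%, 33% or 26%, against 48% with no exclusions in any group.

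### Medical, neurological and non-depressive major Axis I disease are named exclusions for both comparison groups but not for HypoE women, which can bias the unrandomized Aim 1 and 2 contrasts

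*Combined protocol and SAP*

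**What the plan says.** Section C.1.2 of the combined protocol and SAP sets exclusions by group.

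- **Both comparison groups.** The list opens "Exclusion criteria for normal control and postmenopausal groups are current use of hormone contraceptive or any estrogen or progestin therapy, smoking, hypertension, hyperlipidemia, diabetes" and goes on to "medical, neurological, or ophthalmologic disease except acuity problems, a major Axis I disorder other than depression", then recent childbirth or lactation.
- **HypoE.** The list reads "For HypoE women, exclusion criteria includes current use of hormone contraceptive or any estrogen or progestin therapy, allergy to adhesive or tape allergy", with no medical, neurological or psychiatric item.
- **Both lists** close with a discretionary bar on "any concurrent disease or condition that in the opinion of the investigator would make the patient unsuitable for participation in the study".

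The entry criteria shared by HypoE women and controls cover menopausal status, hormone use, language, consent, age and body weight. They contain no medical or psychiatric restriction.

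Two further texts bear on HypoE. C.1.2 states: "All patients with hypothalamic amenorrhea will be diagnosed based on exclusion of other etiologies for their amenorrhea", and lists pregnancy, thyroid dysfunction, hyperprolactinemia, primary ovarian insufficiency and polycystic ovary disease. The definition of FHA in B.6 "excludes pathologic diseases such as those related to a systemic disease".

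On outcomes, Aim 1 names blood pressure, lipids, BMI and inflammatory markers such as hsCRP. C.1.3 collects "metabolic and inflammatory markers (glucose, cortisol, hsCRP") in the study groups. Aim 2 compares PAT across the three groups. C.1.1 plans 30 women per group.

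**The concern.** Aims 1 and 2 are cross-sectional and unrandomized, so they depend on the groups being selected in the same way apart from estrogen status. The plan accepts this in part, since C.1.1 has controls matched on age and BMI. Yet the comparison groups are cleared of general medical, neurological and most major psychiatric illness, and the HypoE group is not. If such illness raises hsCRP or impairs endothelial function, removing it from one side only moves the result in the hypothesized direction for a reason unrelated to estrogen. A finding that HypoE women have worse markers could then reflect screening rather than HypoE.

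The same sentence makes smoking, hypertension, hyperlipidemia and diabetes unequal. Those bear even more directly on Aim 1, because barring hypertension and hyperlipidemia from the comparators selects on outcomes that Aim 1 compares (systolic and diastolic pressure, LDL, HDL, triglycerides).

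**Working it through.** **1. Can anything else in the plan close the gap?**

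| Provision | Where | Effect on the imbalance |
|---|---|---|
| Investigator-opinion clause | C.1.2, both lists | Discretionary, and present on both sides, so it does not offset the extra named items for comparators |
| Diagnosis of exclusion; FHA definition | C.1.2, B.6 | Removes disease that explains the amenorrhea, not unrelated coexisting illness |
| Screening laboratories | C.1.1 | Reproductive, thyroid, prolactin, androgen and pregnancy tests; not designed to find inflammatory, neurological or psychiatric illness |
| Weight limits, age and BMI matching | C.1.1, C.1.2 | Balance age and body size, not illness |
| Statistical adjustment | C.3.5 | The only analysis section is for Aim 3. It points to an Aim 1A for model building, but no section of that name appears. No covariates are stated for Aims 1 and 2 |

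The provisions narrow the gap but do not close it.

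**2. The plan's own figure.** There is no power statement for Aims 1 and 2. The one in C.3.5 is for Aim 3 and reproduces: SD of change = √(2 × 0.44²) = 0.622. With 15 per arm, two-sided α = 0.0167 and 80% power, the detectable difference is 0.775 (stated 0.78). This point does not alter it.

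**3. Illustration for hsCRP.** The only input from the documents is n = 30 per group. Assumed: a share p = 10–20% of HypoE women has an illness barred among comparators, it multiplies hsCRP by k = 2–3, the log-scale SD is 0.8–1.0, and there is no true group difference.

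- Bias on the log scale = p × ln k. Low: 0.10 × ln 2 = 0.069. High: 0.20 × ln 3 = 0.220.
- Geometric-mean ratio = exp(bias): 1.07 to 1.25.
- Standard error = SD × √(2/30): 0.258 at SD 1.0, 0.207 at SD 0.8.
- Bias in standard errors: 0.069/0.258 = 0.27 to 0.220/0.207 = 1.06.
- Two-sided 5% rejection rate (normal approximation): 5.8% to 18.6%.

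The top figure holds the HypoE SD fixed. A 20% subgroup shifted by ln 3 widens it to √(0.8² + 0.2 × 0.8 × (ln 3)²) = 0.91. The standard error becomes √((0.91² + 0.8²)/30) = 0.222, the bias 0.99 standard errors, and the rejection rate about 17%.

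**4. Illustration for PAT.** With the same 10–20% share, an assumed shift of 0.5–1.5 SD in affected women, and the SD of 0.44 from C.3.5, the spurious difference is 0.05–0.30 SD, or 0.02–0.13 PAT units. A two-sided 5% t test with 30 per group, allowing for the widened SD, rejects 5.4% to 18.3% of the time.

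**The case against.** **The barriers on the HypoE side are real.** A systemic illness serious enough to stop menses would disqualify a woman, and the investigator may exclude for any other condition. What remains is unrelated illness that the investigator accepts. This stands, and it is why the point is over-representation. A reader might infer that chronic or psychiatric illness can enter only the HypoE group. The text does not support that: depression is expressly allowed in both comparison groups, and HypoE women do face a discretionary bar.

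**Psychiatric over-representation is not documented.** B.6 says "There are 3 types of FHA associated with stress, weight loss, or excessive exercise" and names no psychiatric disorder. Reading these triggers as evidence of more Axis I illness in HypoE is plausible, but it is inference. The imbalance in the lists is a fact; the imbalance in enrolled women is a possibility.

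**The size is hypothetical.** No prevalence, hsCRP multiplier or log-SD appears in the documents. A two- to threefold multiplier suits active inflammatory disease better than a mixed pool of medical, neurological and psychiatric illness. At the low end nothing of consequence happens. This stands too.

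**Strict alignment has a price.** Stress-associated FHA is one of the types the study covers, and barring Axis I disorders could change who is studied and who is randomized. That weighs against alignment as the only remedy, but not against recording the conditions.

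**Conclusion.** The asymmetry is plain in C.1.2, and nothing else in the plan removes it. Followed as written, the plan can bias the Aim 1 and 2 contrasts on hsCRP and PAT toward HypoE looking worse. The same applies to cortisol if it is compared; C.1.3 collects it, but Aim 1 does not name it. This assumes that the illnesses concerned worsen these markers and occur among enrolled HypoE women. Under the assumed inputs the false-positive rate lies between about 6% and 17–19%. That range shows what could happen and is not an estimate.

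A reader might extend the point to the estradiol trial. That would be wrong: Aim 3 compares arms randomized within HypoE women, so unequal lists between groups do not bias it. The list affects only which HypoE women the Aim 3 result describes.

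The change is worth making because it is cheap and affects what Aims 1 and 2 can conclude.

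**What to change.** **Main change.** At screening, record in every HypoE woman each condition on the list that applies to both comparison groups: medical, neurological and ophthalmologic disease, major Axis I disorder, smoking, hypertension, hyperlipidemia, diabetes, and recent childbirth or lactation. The pre-screening questionnaire described in C.1.1 could carry these items. State in the analysis plan that the Aim 1 and 2 contrasts will be repeated without HypoE women who would have been excluded as comparators, and report both results together.

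**Alternative, where recruitment allows.** Apply the same exclusions to HypoE women. If the wider HypoE population is intended, say so in C.1.2, give the reason, and keep the restricted analysis.

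**Cost.** A short history item, since C.1.3 does not list comorbidity, and fewer HypoE women in the restricted analysis. If 10–20% of 30 are removed (3 to 6 women), the standard error at equal SD rises from √(1/30 + 1/30) = 0.258 SD to √(1/27 + 1/30) = 0.265 or √(1/24 + 1/30) = 0.274 SD, about 3–6%. The loss is larger if smoking and the cardiometabolic conditions are common. Aligning the lists would also shrink the recruitment pool and narrow the population randomized in Aim 3.

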- **C.2.** Specific Aim 2: Is premenopausal HypoE associated with relatively endothelial dysfunction? To establish whether subclinical atherosclerosis is greater in premenopausal HypoE compared to regularly cycling women and recently postmenopausal women using peripheral arterial tonometry (PAT).
- **C.2.1. Data Collection:** Measure of Vascular Function: PAT is a proven, non-invasive measure of vascular function is method of detecting endothelial function by Endo PAT 2000 (Itamar® Medical Ltd), which we and others including the Framingham Study have successfully used. ⁴² The device consists of a finger probe to assess digital volume changes accompanying pulse-waves. A pressure of 40-70mmHg is applied by the probe to the index fingers of both hands to eliminate venous stasis and arterial pulse amplitude is recorded. Device calculates a reactive hyperemia peripheral arterial tonometry (RH-PAT) index, which reflects peripheral vascular function.
- C.3. Specific Aim 3: To determine that estrogen improves CVD inflammatory biomarkers and markers of subclinical CVD in premenopausal HypoE women. In a randomized, double-blind placebo-controlled trial in premenopausal HypoE women we will test 12 weeks of transdermal estradiol on inflammatory biomarkers and subclinical CVD versus placebo at baseline and 12 weeks followed by 2 weeks of estradiol plus progesterone for endometrial safety.
- 30 HypoE women will be randomized to transdermal estrogen for 12 wks followed by transdermal estrogen plus oral progesterone for 2 weeks. We will compare markers of endothelial function and inflammatory response at baseline and 12wks in women randomized to hormone therapy vs placebo.

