with progesterone or placebo pills with placebo patch for 12 weeks +/- 1 week and 2 weeks +/- 3 days after completing estrogen and progesterone (**Figure**). One week after completing the patch and pill, study staff will contact participant and ask if they had their menstrual period. If needed, 1 patch and 3 more pills will be dispensed during the week 12 visit to account for patient schedules if they cannot come in exactly at day 14, as the exit visit on study drug is needed as suggested by the pharmacist.

- **C.3.4. Data Collection:** Serum hormone evaluation: After 7 days of transdermal 17-beta estradiol and 12 weeks we will measure serum E2 levels and hormone panel to assess blood levels and compliance. Vascular measures will be tested at baseline and 12 week. Detailed method collection described under Aim 1A.
- C.3.5. Data Analysis. Statistical method: Associations between change in serum estrogen, change in PAT, change in inflammatory marker levels will be examined. Pearson correlations will be examined between continuous variables. If the distributions are non-normal Spearman correlations will be used. A linear mixed model will be used on the change in PAT at week 12 to examine the association while adjusting for within subject correlation. In addition to choosing an appropriate correlation structure, other model building and diagnostics will be carried out as described in Aim1A. A Tukey-Kramer or Bonferroni adjustment for multiple pair-wise comparisons will be used as appropriate.

Power considerations: Pilot data indicated a baseline SD of 0.35 for PAT in the HypoE group and 0.44 in the control group. Assuming the larger SD at baseline and 4 weeks, a conservative estimate of the SD for the change in PAT assuming no correlation, would be the square root of the sum of the variance estimates at both time points, which is about 0.622. A sample of 15 women in the placebo group and 15 in the treatment group for change in PAT using a two sample t test with 80% power at a significance level of 0.0167 would allow detection of a difference of at least 0.78 units when the sample SD is 0.622. The significance of 0.0167 was chosen by dividing 0.05 by three for the number of comparisons between groups. Increasing correlation above zero between pre and post PAT values will give more precision and allow detection of smaller differences (e.g. a correlation of 0.8 allows detection of a difference of at least 0.35 units).

References:

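### The Aim 3 PAT model in C.3.5 names neither randomised arm nor baseline PAT; with equal SDs, adding the baseline would cut treatment-effect variance by 6.5% (r = 0.8) to 48% (r = 0) for one degree of freedom

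*Combined protocol and SAP*

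**What the plan says.** Section C.3 of the combined protocol and SAP sets out a randomised comparison: "We will compare markers of endothelial function and inflammatory response at baseline and 12wks in women randomized to hormone therapy vs placebo". The statistical-method text in C.3.5 does not turn this into a model with stated terms. It begins with "Associations between change in serum estrogen, change in PAT, change in inflammatory marker levels will be examined", using Pearson or Spearman correlations. It then says "A linear mixed model will be used on the change in PAT at week 12 to examine the association", with an adjustment for correlation within each woman. For the rest, "other model building and diagnostics will be carried out as described in Aim1A"; the documents contain no section of that name, and the Aim 1 section has no analysis text.

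C.3.4 says that vascular measures "will be tested at baseline and 12 week", and C.3.3 places the baseline collection before randomisation.

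The power paragraph in C.3.5 uses a two-sample t test on change in PAT, 15 women per arm, 80% power and alpha 0.0167 (0.05/3). Its SD of 0.622 is described as "a conservative estimate of the SD for the change in PAT assuming no correlation" and gives a detectable difference of 0.78. It adds that "a correlation of 0.8 allows detection of a difference of at least 0.35 units".

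**The concern.** The mixed-model sentence can be read in two ways.

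- **Taken literally**, the outcome is one week-12 change per woman. There is then no repeated outcome, so no within-subject correlation to adjust for and no correlation structure to choose.
- **Taken as a repeated-measures model** of both visits with arm by visit, complete data give the same treatment estimate and standard error as the unadjusted change score.

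Neither reading gains the precision that baseline adjustment offers. The correlations among changes do not estimate the effect of randomised treatment at all.

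With 15 women per arm and alpha already reduced to 0.0167, precision is scarce. As written, two competent analysts could also fit different models to the same Aim 3 PAT data.

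**Working it through.** **Inputs** (C.3.5 power paragraph): n = 15 per arm; two-sided alpha 0.05/3 = 0.0167; power 80%; PAT SD s = 0.44 at both time points (pilot control group; the pilot HypoE SD is 0.35); pre-post correlation r, for which the plan uses 0 and 0.8. The plan does not state sidedness, but the two-sided t test is the version that reproduces its figures.

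**Step 1: reproduce the plan.** The SD of change is s·√(2(1−r)).

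- r = 0: 0.44·√2 = 0.622.
- r = 0.8: 0.44·√0.4 = 0.278.

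The detectable difference is δ·SD·√(2/15), where δ is the noncentrality giving 80% power. From the noncentral t with 28 df, δ ≈ 3.411, and √(2/15) = 0.3651.

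- r = 0: 3.411 × 0.6223 × 0.3651 = 0.775 (plan: 0.78).
- r = 0.8: 3.411 × 0.2783 × 0.3651 = 0.347 (plan: 0.35).

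**Step 2: add baseline PAT.** The residual SD becomes s·√(1−r²), with 27 df. Chance baseline imbalance multiplies the variance on average by 1 + 1/(30−4) = 27/26 for normal data. The noncentrality is now about 3.418.

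- r = 0: 3.418 × 0.44 × √(27/26) × 0.3651 = 0.560.
- r = 0.8: the same multiplied by √(1−0.64) = 0.6, which is 0.336.

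**Step 3: variance ratio, adjusted to unadjusted.**

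[s²(1−r²)·27/26] / [2s²(1−r)] = (1+r)/2 × 27/26

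| r | Detectable, change score | Detectable, adjusted | Variance saving |
|---|---|---|---|
| 0 | 0.775 | 0.560 | 48.1% |
| 0.3 | 0.649 | 0.534 | 32.5% |
| 0.5 | 0.548 | 0.485 | 22.1% |
| 0.7 | 0.425 | 0.400 | 11.7% |
| 0.8 | 0.347 | 0.336 | 6.5% |
| 0.95 | 0.173 | 0.175 | −1.3% |

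The detectable differences cross at r ≈ 0.92 and the variances at r ≈ 0.93. With s = 0.35 at both visits, the pairs are 0.617 and 0.445 (r = 0), 0.436 and 0.386 (r = 0.5), and 0.276 and 0.267 (r = 0.8), with the same percentage savings.

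**Step 4: simulation.** With 100,000 normal trials per value of r, the savings were 48.3% (r = 0) and 6.8% (r = 0.8). With 20,000 trials per row, at the effect the adjusted model should detect with 80% power:

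| r | Effect | Power, change score | Power, adjusted |
|---|---|---|---|
| 0 | 0.560 | 0.476 | 0.802 |
| 0.5 | 0.485 | 0.677 | 0.796 |
| 0.8 | 0.336 | 0.768 | 0.795 |

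**Step 5: the two readings of the mixed model.** In one simulated complete data set, a random-intercept model with arm by visit gave a treatment effect of 0.5785 (SE 0.1898), identical to the difference in mean change. Once baseline was a covariate, the arm coefficient was 0.4280 whether the outcome was week-12 PAT or change. This follows from the algebra: subtracting baseline from the outcome only lowers the baseline coefficient by 1.

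**The case against.** **The arm contrast is already in the plan.** C.3 states it, and the power paragraph gives groups, outcome, test and alpha. This stands as far as intent goes: the plan does not lack a between-arm comparison. But the t test is given as a planning device, and the analysis text names a different model without its terms.

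**The change score is valid, so this is only about efficiency.** True; no bias is claimed.

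**The 48% end is implausible.** The plan offers r = 0 as a conservative bound, and at r = 0.8 the change score has 77% power against 80%. This is fair. With no observed correlation in the documents, the trial cannot be placed within the range, so the savings should be reported across r.

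**The savings depend on equal SDs.** This also stands. As an illustration (an assumption, using the two pilot SDs), take 0.35 at baseline and 0.44 at week 12. The saving is then 36% at r = 0 and 7% at r = 0.5, and becomes a 3.8% loss at r = 0.8. In the reverse order it is 60%, 41% and 34%. The downside is bounded: the expected loss is greatest when the baseline slope equals 1, where only the imbalance factor remains, and 27/26 − 1 = 3.8%. The plan itself assumes equal SDs.

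**A baseline term may have been intended under Aim1A.** Possibly, but the current documents do not show it.

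**Conclusion.** The concern holds. The Aim 3 model as written identifies neither the treatment term nor a baseline covariate, and the power calculation rests on an unadjusted change score. Under the plan's own inputs, baseline adjustment saves between 6.5% (r = 0.8) and 48% (r = 0) of the treatment-effect variance, at a cost of one degree of freedom.

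These figures assume normal data, equal SDs at the two visits and no dropout. The true r is unknown; with equal SDs the gain ends at about 0.92. If the SDs differ, the gain may be larger or smaller, and the expected variance penalty does not exceed about 4%. This is an improvement the sponsor should make; the existing comparison remains valid without it.

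**What to change.** In C.3.5, specify the Aim 3 PAT analysis as a linear model with randomised arm and baseline PAT. Either week-12 PAT or change may be the outcome, since the treatment estimate is the same. Let this replace the mixed model on a single change value; if a two-visit model was meant, write out its terms.

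Restate the detectable difference over a range of r, using SD 0.44·√(1−r²), 27 df and the 27/26 variance allowance. Use the same arm-plus-baseline form for inflammatory markers such as hsCRP, log-transformed if skewed; no gain can be quantified there because the documents give no SD or correlation. In the same edit, label the change-change correlations as exploratory and write out or delete the Aim1A reference.

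The cost is wording and one degree of freedom. No extra visit or measurement is needed.
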